## 5 INVESTIGATIONAL PLAN

### 5.1 Study Design

Proposed is a randomized (1:1) prospective trial to determine changes in VO2peak in patients with treatment-naïve mRCC treated with sunitinib therapy on two different common schedules (see **Section 2**). Patients randomized to sunitinib schedule 4/2 (**Arm A**) will receive sunitinib at 50 mg daily for 4 weeks on, followed by 2 weeks off, per standard of care. Patients randomized to sunitinib schedule 2/1 (**Arm B**) will receive sunitinib 50 mg daily for 2 weeks on, followed by 1 week off. All subjects will undergo detailed functional capacity assessments at baseline, 4-5 weeks, and after 12 weeks.

Specific recommendations for management of possible AEs, along with guidelines for dose delay/modification or discontinuation from study treatment are provided in this section, based on best evidence from contemporary trials and retrospective studies.

#### 5.1.1 Dose Modification

Dose interruptions or reductions of sunitinib may be required following potential drug-related toxicities. Fatigue, generalized muscle weakness, mucositis/stomatitis, hypertension, hand-foot syndrome, bleeding, vascular thrombosis, thrombocytopenia/neutropenia, and other AEs have been reported in response to treatment with sunitinib.

At each visit during the Treatment Period, subjects should first be evaluated for the occurrence of AEs and laboratory abnormalities. Specific recommendations for management of possible AEs, other than hepatotoxicity, along with guidelines for dose delay/modification or discontinuation of study treatment, are adapted from Kollmannsberger et al., and are provided in **Table 1**. In the event of treatment-emergent hepatotoxicity, please follow the guidelines for management hepatotoxicity provided in **Table 2**. For toxicities unrelated to sunitinib, dose modifications and holds are per the discretion of the investigator.

If dose reduction is necessary, two dose reductions are permitted in a stepwise fashion (initially to 37.5 mg and subsequently to 25 mg if necessary); however, the schedule (4/2 vs. 2/1) will not be changed during the study period. If the toxicity does not recur or worsen, the dose can then be increased stepwise back to the next dose level (37.5 mg or 50 mg as appropriate) at the start of the next treatment cycle. Increases to the next dose level should only be initiated at the start of the next treatment cycle, not during a treatment cycle.

**Table 1 Dose Modification Algorithms for Potential Treatment-Related Adverse Events (AEs)**

AE Terms & Descriptions	Dose Modification Algorithms	
	Sunitinib 4/2	Sunitinib 2/1
Hypertension (Scenario)		
(A). Asymptomatic and persistent systolic blood pressure (SBP) of $\geq 150$ and $< 170$ mmHg, or diastolic blood pressure (DBP) of $\geq 90$ and $< 110$ mmHg, or a clinically significant increase in DBP of $\geq 20$ mmHg.	Step 1. Continue study treatment at same dose. Step 2. Adjust current dose of or initiate new antihypertensive medication(s). Step 3. Titrate antihypertensive medication(s) during next 2 weeks as indicated to achieve well-controlled  blood pressure (BP). If BP is not well-controlled within 2 weeks, follow Step 1 in scenario (B) below.	Step 1. Continue study treatment at same dose. Step 2. Adjust current dose of or initiate new antihypertensive medication(s). Step 3. Titrate antihypertensive medication(s) during next 2 weeks as indicated to achieve well-controlled  blood pressure (BP). If BP is not well-controlled within 2 weeks, follow Step 1 in scenario (B).
(B). Symptomatic, or SBP $\geq 170$ mmHg, or DBP $\geq 110$ mmHg, or failure to achieve well-controlled BP within 2 weeks in scenario (A).	Step 1. Interrupt study treatment. Step 2. Adjust current or initiate new antihypertensive medication(s). Step 3. Titrate antihypertensive medication(s) during next 2 weeks as indicated to achieve well-controlled BP. Step 4. Restart study treatment at same dose or lower dose at discretion of investigator  once BP is well-controlled.  Dose adjustment or discontinuation of antihypertensive medication(s) may be necessary during scheduled 2-week off treatment period.	Step 1. Interrupt study treatment. Step 2. Adjust current or initiate new antihypertensive medication(s). Step 3. Titrate antihypertensive medication(s) during next 2 weeks as indicated to achieve well-controlled BP. Step 4. Restart study treatment at same dose or lower dose at discretion of investigator  once BP is well-controlled.  Dose adjustment or discontinuation of antihypertensive medication(s) may be necessary during scheduled 1-week off treatment period.
(C). Two or more symptomatic episodes of hypertension despite modification of antihypertensive medication(s) and reduction of study medication dose.	Discontinue study treatment and follow up per protocol.	Discontinue study treatment and follow up per protocol.
Cardiac Toxicity		
Grade 1	Continue at same dose level	Continue at same dose level
Grade 2	Continue at same dose level. OR If asymptomatic decrease of LVEF by absolute value of 20% and to $< LLN$ or nonurgent ventricular paroxysmal dysrhythmia requiring intervention: Step 1. Interrupt study treatment until toxicity reduced to $\leq$ Grade 1. Step 2. Restart treatment with lower dose  ; monitor as clinically indicated.	Continue at same dose level. OR If asymptomatic decrease of LVEF by absolute value of 20% and to $< LLN$ or nonurgent ventricular paroxysmal dysrhythmia requiring intervention: Step 1. Interrupt study treatment until toxicity reduced to $\leq$ Grade 1. Step 2. Restart treatment with lower dose  ; monitor as clinically indicated.
Grade 3	Step 1. Interrupt study treatment until toxicity reduced to $\leq$ Grade 1. Step 2. Restart treatment with lower dose  ; monitor as clinically indicated.	Step 1. Interrupt study treatment until toxicity reduced to $\leq$ Grade 1. Step 2. Restart treatment with lower dose  ; monitor as clinically indicated.
Grade 4	Discontinue study treatment and follow up per protocol.	Discontinue study treatment and follow up per protocol.

AE Terms & Descriptions	Dose Modification Algorithms	
	Sunitinib 4/2	Sunitinib 2/1
Proteinuria		
Urine Protein Creatinine Ratio (UPC) <3	Continue study treatment at same dose. Monitor as clinically indicated.	Continue study treatment at same dose. Monitor as clinically indicated.
UPC ≥3	
Step 1: Obtain a 24-hr urine protein.
 
Step 2: If 24-hour urine protein is <3 g, subject may continue treatment at same dose.
 
OR
 
If 24-hour urine protein is ≥3 g, interrupt treatment until UPC returns. to <3. Restart therapy at lower dose. Monitor UPC for the remainder of the overall treatment period. If UPC ≥3, obtain a 24- hour urine protein.
 
Step 3: If 24-hour urine protein is ≥3 g, following repeat dose reductions, discontinue treatment and follow up per protocol.
	
Step 1: Obtain a 24-hr urine protein.
 
Step 2: If 24-hour urine protein is <3 g, subject may continue treatment at same dose.
 
OR
 
If 24-hour urine protein is ≥3 g, interrupt treatment until UPC returns. to <3. Restart therapy at lower dose. Monitor UPC for the remainder of the overall treatment period. If UPC ≥3, obtain a 24- hour urine protein.
 
Step 3: If 24-hour urine protein is ≥3 g, following repeat dose reductions, discontinue treatment and follow up per protocol.

Hemorrhage/Bleeding/Coagulopathy		
Grade 1	Continue study treatment at same dose. Monitor as clinically indicated.	Continue study treatment at same dose. Monitor as clinically indicated.
Grade 2	
Step 1. Interrupt study treatment until the AE resolves to ≤ Grade 1.
 
Step 2. Restart treatment with lower dose; monitor as clinically indicated.
	
Step 1. Interrupt study treatment until the AE resolves to ≤ Grade 1.
 
Step 2. Restart treatment with lower dose; monitor as clinically indicated.

Grade 3 or 4, or Recurrent ≥Grade 2 event after dose interruption/reduction.	
Discontinuation of study treatment and follow up per protocol.
 
Note: If abnormality is not clearly associated with clinical consequences, contact the Duke PI to discuss the potential for continuation of study treatment. If agreed, subject may restart treatment at lower dose.
	
Discontinuation of study treatment and follow up per protocol.
 
Note: If abnormality is not clearly associated with clinical consequences, contact the Duke PI to discuss the potential for continuation of study treatment. If agreed, subject may restart treatment at lower dose.

AE Terms & Descriptions	Dose Modification Algorithms	
	Sunitinib 4/2	Sunitinib 2/1
Venous Thrombosis		
Grade 2	Continue study treatment with same dose; monitor as clinically indicated.	Continue study treatment with same dose; monitor as clinically indicated.
Grade 3 or asymptomatic Grade 4	
Step 1. Interrupt study treatment.
 
Step 2. Start to treat the subject with an anticoagulant.
 
Step 3. Resume study treatment at same dose during the period of full-dose anticoagulation if all of the following criteria are met:
 
 
• The subject must have been treated with anticoagulant for at least one week.
 
• No Grade 3 or 4 hemorrhagic events have occurred while on anticoagulation treatment.
 
• Subject should be monitored as clinically indicated during anticoagulation treatment and after resuming study treatment.
 
	
Step 1. Interrupt study treatment.
 
Step 2. Start to treat the subject with an anticoagulant.
 
Step 3. Resume study treatment at same dose during the period of full-dose anticoagulation if all of the following criteria are met:
 
 
• The subject must have been treated with an anticoagulant for at least one week.
 
• No Grade 3 or 4 hemorrhagic events have occurred while on anticoagulation treatment.
 
• Subject should be monitored as clinically indicated during anticoagulation treatment and after resuming study treatment.
 

Symptomatic Grade 4	Discontinuation of study treatment and follow up per protocol.	Discontinuation of study treatment and follow up per protocol
Arterial Thrombosis		
Any Grade	Discontinuation of study treatment and follow up per protocol.	Discontinuation of study treatment and follow up per protocol
Neutropenia		
Grade 1 or 2	Continue study treatment at same dose; monitor as clinically indicated.	Continue study treatment at same dose; monitor as clinically indicated.
Grade 3 lasting $\geq$ 5 days	
Step 1. Interrupt study treatment until toxicity reduced to <math>\leq</math> Grade 2.
 
Step 2. Restart study treatment at same dose.
	
Step 1. Interrupt study treatment until toxicity reduced to <math>\leq</math> Grade 2.
 
Step 2. Restart study treatment at same dose.

Grade 4	
Step 1. Interrupt study treatment until toxicity reduced to <math>\leq</math> Grade 2.
 
Step 2. Restart study treatment with lower dose.
	
Step 1. Interrupt study treatment until toxicity reduced to <math>\leq</math> Grade 2.
 
Step 2. Restart study treatment with lower dose.

Recurrent Grade 3/4 event after initial dose reduction	
Step 1. Interrupt study treatment until toxicity reduced to <math>\leq</math> Grade 2.
 
Step 2. Restart study treatment with lowest dose (25 mg/day).
	
Step 1. Interrupt study treatment until toxicity reduced to <math>\leq</math> Grade 2.
 
Step 2. Restart study treatment with lowest dose (25 mg/day).

AE Terms & Descriptions	Dose Modification Algorithms	
	Sunitinib 4/2	Sunitinib 2/1
Thrombocytopenia		
Grade 1 or 2	Continue study treatment at same dose; monitor as clinically indicated.	Continue study treatment at same dose; monitor as clinically indicated.
Grade 3 lasting $\geq$ 5 days	Step 1. Interrupt study treatment until toxicity reduced to $\leq$ Grade 2. Step 2. Restart study treatment with lower dose. 	Step 1. Interrupt study treatment until toxicity reduced to $\leq$ Grade 2. Step 2. Restart study treatment with lower dose. 
Grade 4	Step 1. Interrupt study treatment until toxicity reduced to $\leq$ Grade 2. Step 2. Restart study treatment with lower dose. 	Step 1. Interrupt study treatment until toxicity reduced to $\leq$ Grade 2. Step 2. Restart study treatment with lower dose. 
Recurrent Grade 3/4 event after initial dose reduction	Step 1. Interrupt study treatment until toxicity reduced to $\leq$ Grade 2. Step 2. Restart study treatment with lowest dose (25 mg/day).	Step 1. Interrupt study treatment until toxicity reduced to $\leq$ Grade 2. Step 2. Restart study treatment with lowest dose (25 mg/day).
Fatigue (lethargy, malaise, generalized muscle weakness)		
Grades 1 and 2	Continue study treatment at same dose; monitor as clinically indicated	Continue study treatment at same dose; monitor as clinically indicated.
Grades 3 and 4	Step 1. Interrupt study treatment until toxicity reduced to $\leq$ Grade 2. Step 2. Restart study treatment at lower dose. 	Step 1. Interrupt study treatment until toxicity reduced to $\leq$ Grade 2. Step 2. Restart study treatment at lower dose. 
Hand-foot Syndrome		
Grades 1 and 2	Continue study treatment at same dose; monitor as clinically indicated.	Continue study treatment at same dose; monitor as clinically indicated.
Grade 3	Step 1. Interrupt study treatment until toxicity reduced to $\leq$ Grade 1. Step 2. Restart study treatment at same dose or lower dose at discretion of investigator. 	Step 1. Interrupt study treatment until toxicity reduced to $\leq$ Grade 1. Step 2. Restart study treatment at same dose or lower dose at discretion of investigator. 
Grade 4	Step 1. Interrupt study treatment until toxicity reduced to $\leq$ Grade 2. Step 2. Restart study treatment at lower dose or discontinue at discretion of investigator. 	Step 1. Interrupt study treatment until toxicity reduced to $\leq$ Grade 2. Step 2. Restart study treatment at lower dose or discontinue at discretion of investigator. 
Anemia: Note: No dose reduction rules are indicated for anemia unless due to hemorrhage or bleeding as noted above		

AE Terms & Descriptions	Dose Modification Algorithms	
	Sunitinib 4/2	Sunitinib 2/1
Other Clinically Significant Adverse Events		
Grade 1 or 2	Continue study treatment at same dose; monitor as clinically indicated.	Continue study treatment at same dose; monitor as clinically indicated
Grade 3	Step 1. Interrupt study treatment until toxicity reduced to ≤Grade 1. Step 2. Restart study treatment at same dose or lower dose at discretion of investigator. 	Step 1. Interrupt study treatment until toxicity reduced to ≤Grade 1. Step 2. Restart study treatment at same dose or lower dose at discretion of investigator. 
Recurrent Grade 3	Step 1. Interrupt study treatment until toxicity reduced to ≤Grade 1. Step 2. Restart study treatment at lower dose. 	Step 1. Interrupt study treatment until toxicity reduced to ≤Grade 1. Step 2. Restart study treatment at lower dose. 
Grade 4	Step 1. Interrupt study treatment until toxicity reduced to ≤Grade 2. Step 2. Restart study treatment at lower dose or discontinue at discretion of investigator. 	Step 1. Interrupt study treatment until toxicity reduced to ≤Grade 2. Step 2. Restart study treatment at lower dose or discontinue at discretion of investigator. 

1. Well-controlled BP defined as mean SBP <150 mmHg and mean DBP <90 mmHg. See **Appendix F: Recommendations for Management of Hypertension**.

2. Sunitinib dose should be reduced by 12.5 mg (i.e., 50 mg to 37.5 mg or 37.5 mg to 25 mg), but the schedule (i.e., 4/2 or 2/1) MUST be maintained.

3. See **Section 5.2.1** for additional guidelines on management of fatigue and generalized muscle weakness.

4. Adverse events are graded according to NCI Common Terminology Criteria for Adverse Events v4.0

Abbreviations: SBP, systolic blood pressure; DBP, diastolic blood pressure; BP, blood pressure.

### 5.1.2 Dose Modifications and Management of Liver Toxicity

In the event of treatment-emergent hepatotoxicity, potential contributing factors such as concomitant medications, viral hepatitis, choledocholithiasis, and hepatic metastases should be investigated. Concomitant medications known to be hepatotoxic that may be contributing to liver dysfunction should be discontinued or replaced with alternative medications to allow for recovery of liver function. As generally understood, ALT  $>3$  x upper limit of normal (ULN) and concomitant bilirubin  $\geq 2.0$  x ULN ( $>35\%$  direct bilirubin), in the absence of elevated alkaline phosphatase or biliary injury, suggest significant liver injury. See **Table 2: Guidelines for Management of Treatment-Emergent Hepatotoxicity**.

**Table 2 Guidelines for Management of Treatment-Emergent Hepatotoxicity**

AE Terms & Descriptions	Dose Modification Algorithms
(A). ALT of $\leq 3.0$ x ULN	Continue study treatment with full-panel liver function tests (LFTs)  monitored as per protocol.
(B). ALT $>3.0$ x ULN to $\leq 8.0$ x ULN without bilirubin elevation (defined as total bilirubin $<2.0$ x ULN or direct bilirubin $\leq 35\%$ ) and without hypersensitivity symptoms (e.g., fever, rash)	Continue study treatment. Perform the following assessments for excluding hypersensitivity and other contributing factors: 
 
• Eosinophil count
 
• Viral serology for hepatitis A, B, and C
 
• Liver imaging
 
 Monitor subject closely for clinical signs and symptoms; perform full-panel LFTs  weekly or more frequently if clinically indicated until ALT/AST reduced to Grade 1. If the subject is withdrawn from study treatment, follow up per protocol.
(C). ALT $>3.0$ x ULN with concomitant elevation in bilirubin (defined as total bilirubin $\geq 2.0$ x ULN; with direct bilirubin $>35\%$ ) or with hypersensitivity symptoms (e.g., fever, rash) Or (D). ALT $>8.0$ x ULN without concomitant elevation in bilirubin (defined as total bilirubin $\geq 2.0$ x ULN; with direct bilirubin $>35\%$ )	Discontinue study treatment immediately. Consult a hepatologist, and perform the following assessments to identify co-contributing factors: 
 
• Eosinophil count
 
• Viral serology for hepatitis A, B, C, and E; cytomegalovirus (CMV); Epstein-Barr virus (EBV IgM antibody, or heterophile antibody, or monospot testing); anti-nuclear antibody (ANA); anti-smooth muscle antibody (SMA); and anti-mitochondrial antibody
 
• Serum creatinine phosphokinase (CPK) for possible muscle injury
 
• LFT elevation
 
• Liver imaging (ultrasound or CT scan)
 
 Monitor subject closely for clinical signs and symptoms; perform full-panel LFTs  weekly or more frequently if clinically indicated until LFTs reduced to Grade 1.
Isolated total bilirubin elevation without concurrent ALT elevation (defined as ALT $<3$ x ULN)	Step 1. Perform bilirubin fractionation at any time when total bilirubin is $\geq 1.5$ X ULN. Continue dosing at full dose, and perform weekly LFT assessments  until total bilirubin return to $\leq 1.5$ x ULN.

1. Full-panel LFTs include: AST, ALT, alkaline phosphatase,  $\gamma$ -GT, and total bilirubin. If at any time the total bilirubin is  $> 1.5$  x ULN, perform bilirubin fractionation for direct and indirect bilirubin.

**Note:** Because many subjects are taking multiple concurrent medications, it is critical to do a thorough evaluation of the subject's concurrent medications, identify and discontinue those with known hepatotoxicity, and replace with a non-hepatotoxic equivalent for the same indication if necessary.

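### Table 2 has no written hold point for a severe, mainly direct bilirubin rise attributed to sunitinib when ALT is below 3 × ULN

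*Combined protocol and SAP*

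**What the plan says.** Section 5.1.1 divides toxicity management between two tables. Table 1 is introduced with "Specific recommendations for management of possible AEs, other than hepatotoxicity", and treatment-emergent hepatotoxicity is sent to Table 2. The section opens by accepting that drug-related toxicity can call for interrupting or reducing sunitinib. Its explicit grant of discretion over holds reads "For toxicities unrelated to sunitinib, dose modifications and holds are per the discretion of the investigator".

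The last row of Table 2 covers a raised total bilirubin with ALT below 3 × ULN. Its single numbered step asks for fractionation once total bilirubin reaches 1.5 × ULN, then says "Continue dosing at full dose, and perform weekly LFT assessments" until the value is 1.5 × ULN or lower. Footnote 1 defines the panel (AST, ALT, alkaline phosphatase, γ-GT and total bilirubin) and repeats the instruction to "perform bilirubin fractionation for direct and indirect bilirubin", here for values above 1.5 × ULN. Row A, for ALT up to 3.0 × ULN, continues treatment and has no bilirubin condition. Rows C and D share the one stop instruction in the table: "Discontinue study treatment immediately. Consult a hepatologist".

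Section 5.1.2 adds that "potential contributing factors such as concomitant medications, viral hepatitis, choledocholithiasis, and hepatic metastases should be investigated" and that hepatotoxic concomitant drugs should be stopped or replaced. It sets no hold for sunitinib. Section 8.8.1 lets the principal investigator withdraw a subject, with adverse events and abnormal laboratory values among the listed reasons.

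**The concern.** The isolated-bilirubin row gives the same advice however high the bilirubin goes. Fractionation is requested, yet a mainly direct result and a mainly indirect result lead to the same dosing. Elsewhere the plan treats the direct fraction as informative: rows B and C are separated partly by whether it exceeds 35%.

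The stake is patient safety. A clinician with a patient whose bilirubin reaches Grade 3 or 4, is mainly direct, and is thought to come from sunitinib would find advice to carry on at full dose. No written point for holding and restarting would support a more cautious course. The words for full dose are also unclear for a patient already reduced to 37.5 or 25 mg under Section 5.1.1.

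**Working it through.** There is no figure to recompute. The check sets the rules side by side.

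**1. Table 2 by ALT and bilirubin (multiples of ULN).**

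| ALT | Bilirubin condition | Row | Advice |
|---|---|---|---|
| ≤3.0 | none | A | continue |
| <3 | total raised | isolated bilirubin | continue at full dose |
| >3.0 to 8.0 | total <2.0, or direct ≤35%; no hypersensitivity | B | continue |
| >3.0 | total ≥2.0 with direct >35%, or hypersensitivity | C | discontinue |
| >8.0 | without the row C bilirubin rise | D | discontinue |

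Two rows apply at ALT below 3. Both continue treatment (2 of 2), neither has a bilirubin ceiling (0 of 2), and neither has a hold or stop step (0 of 2). With ALT below 3, total bilirubin of 2, 5 or 10 × ULN (illustrative values) gets the same advice. The weekly panel can move the patient to row C, but only once ALT exceeds 3.0.

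**2. Could another rule supply the hold?**
- Table 1, Other Clinically Significant Adverse Events, interrupts at Grades 3 and 4. Section 5.1.1 routes hepatotoxicity to Table 2, so this row does not clearly apply.
- The explicit discretion over holds covers unrelated toxicity. A rise traced to choledocholithiasis would qualify; one attributed to sunitinib would not.
- The opening of Section 5.1.1 recognises interruptions and reductions for drug-related toxicity in general, without a bilirubin threshold.
- Section 8.8.1 permits withdrawal, again without a threshold or a hold-and-restart step.

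**3. Comparison with Table 1.** Nine AE categories are defined by grade: cardiac, hemorrhage, venous thrombosis, arterial thrombosis, neutropenia, thrombocytopenia, fatigue, hand-foot syndrome and other. All 9 interrupt or stop at Grade 4. Seven do so at any Grade 3, and the other two (neutropenia and thrombocytopenia) do so when Grade 3 lasts at least 5 days: 7 + 2 = 9. Anemia is a stated exception, so counting it gives 9 of 10 at Grade 4.

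**4. Which hold condition fits Table 2?** Take a Grade 3 bilirubin, assumed to be at least 2.0 × ULN because the documents do not print the CTCAE cut-offs, with no hypersensitivity symptoms and no documented unrelated cause.

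| Direct fraction | ALT 5 × ULN (current rule) | ALT 2 × ULN, hold at any fraction | ALT 2 × ULN, hold only if direct >35% |
|---|---|---|---|
| ≤35% | continue (row B) | hold | continue |
| >35% | discontinue (row C) | hold | hold |

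A hold at any fraction would treat the lower-ALT patient more strictly than row B does. Tying the hold to a direct fraction above 35% removes that conflict.

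**The case against.** The best reply is that nothing bars a hold. Table 2 is titled as guidelines, and Section 5.1.1 foresees interruption for drug-related toxicity. Row B advises continuing yet provides for a subject taken off study treatment, so advice to continue does not forbid stopping. Sections 8.7 and 8.8.2 provide for discontinuing study drug for any reason. This stands. A reader might infer that the protocol compels full dosing, or that withdrawal from the study is the only way out; these passages support neither inference.

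Second, Section 5.1.2 describes significant liver injury as raised ALT together with raised, more than 35% direct bilirubin, and row B discounts mainly indirect bilirubin. Lenient handling of an isolated rise may be deliberate. That stands for mainly indirect rises. It does not explain why a severe, mainly direct rise has no hold point.

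Third, the comparison with Table 1 mixes clinical events with laboratory values. Of its three blood-count entries, none holds at any Grade 3, and anemia has no dose-reduction rule unless it is due to bleeding. This weakens the Grade 3 comparison. At Grade 4, neutropenia and thrombocytopenia still interrupt, and the anemia exception is written out, whereas the bilirubin row gives no reason.

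Fourth, every other cell in Tables 1 and 2 with a Step 1 also has a Step 2, so a step may be missing from this copy. The cell has its own end condition and reads as complete, but a lost step cannot be excluded.

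**Conclusion.** The point holds as a narrow gap in the written safety guidance. At ALT below 3 × ULN, no bilirubin value alone leads to a hold or stop in Table 2, and no other section gives a threshold for a severe, mainly direct rise attributed to sunitinib. Clinical judgement remains open, but it has no written hold point to rely on.

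The practical size is probably small. The documents give no frequency for isolated bilirubin rises. Entry requires total bilirubin of 1.5 × ULN or less, study treatment runs from Day 1 to Day 85, and planned accrual is 36.

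A reader might also infer harm to the primary result. The documents do not support that: nothing in this row enters the paired t-test of VO2peak or the sample-size calculation. The change is optional. The conclusion assumes that the cell is complete as it stands.

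**What to change.** First confirm against the source table that no Step 2 is missing. If none is, add:

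> *Step 2. If total bilirubin is CTCAE v4.0 Grade 3 or 4 with direct bilirubin >35% and no cause unrelated to sunitinib is documented, follow the Grade 3, recurrent Grade 3 and Grade 4 lines of Other Clinically Significant Adverse Events in Table 1, and investigate the contributing factors listed in 5.1.2. If direct bilirubin is ≤35%, continue at the current dose with weekly full-panel LFTs, with any hold at the investigator's discretion.*

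In Step 1, change full dose to current dose. In row A, add a pointer: *for total bilirubin >1.5 × ULN, see the isolated-bilirubin row*. Two boundaries can be tidied in the same edit. Set the row's ALT condition to ≤3.0 × ULN so that the pointer works at exactly 3.0, and align the fractionation trigger, which is ≥1.5 in the row and >1.5 in footnote 1.

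The cost is two reworded rows in an amendment. No scheduled test, visit or analysis is added, since fractionation, weekly panels and the search for contributing factors are already requested. The hold and restart rules and the grading scale are the plan's own. That includes a Table 1 oddity the sponsor may wish to review: Grade 3 must recover to Grade 1 or less before restart, but Grade 4 only to Grade 2 or less. The downside is an occasional extra hold, which would slightly lower recorded dose intensity.
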